In an mRS mean change analysis, the subjects in the treatment group experienced a mean change of 2.5 points, compared to 1.3 points in the sham group ($P < 0.001$). When comparing to peer-reviewed publications and published datasets addressing populations comparable to that enrolled in the BQ3 study (baseline mRS of 3-4), the observational (48) and placebo (46, 47) groups perform similarly to BQ3 sham group (Figure 3). By derivation, despite the fact that the BQ3 study enrolled a small number of subjects for statistically-significant conclusions to be drawn, the sham group performed as expected from historical data, while the treatment group substantially outperformed the control groups in the published evidence.

[figure not shown]

Figure 3. Modified Rankin Scale change in the treatment and control groups of the BQ3 study compared to historical control

An mRS improvement of 2 or more points was observed in 92% of the treatment group subjects, while an improvement of 3 mRS points was found in 54% of the treatment group subjects. Only 25% of the sham group subjects improved by 2 points and a 3-point improvement was not reported in any of the subjects. Individual point shifts can be seen in [Figure 4](#) below.

[figure not shown]

Figure 4. Parallel coordinates plot showing individual changes in mRS from sub-acute phase to 70 days post-stroke in the BQ3 study

To better assess the magnitude of this kind of effect, the mean mRS difference between baseline and post-stroke day 90 mRS obtained with the BQ treatment was compared with its counterpart reported for all the currently recommended acute phase ischemic stroke therapies ([Figure 5](#)).

[figure not shown]

Figure 5. Observed mean difference effect in mRS at 90 days (treatment group – control/placebo group) post-stroke for different acute treatments, compared to the BQ treatment.

The data presented are derived from Saver 2007 (62); thrombectomy data is reproduced from Goyal et al 2016 (16); data on Aspirin is based on a 4-level version of the mRS used in the International Stroke Trial (IST; (63)) and the Chinese Acute Stroke Trial (CAST; (64)), rather than the full 7-level mRS.

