4 STUDY DESIGN

4.1 OVERALL DESIGN

- Type of trial: prospective, multicenter, double-blind, randomized, sham-controlled, parallel two-arm study following a sample-size–adaptive design with a single planned interim analysis (for details of the interim analysis, please refer to § 9.4.6).
- Statement of hypothesis: improvement in mRS score from baseline to 90 days post-stroke will be greater in patients allocated to active stimulation (BQ 2.0 group) than in patients allocated to sham stimulation (sham) group.

	The efficacy of a frequency-tuned electromagnetic field treatment in facilitating the recovery of subacute ischemic stroke patients – a pivotal study		
	No. BQ5	Ver. 4	Page 37 of 150

- Sample size and allocation: 150 subjects¹⁸ assigned at 1:1 allocation ratio to either active or sham group.
- Study population: ischemic stroke subjects with upper limb motor impairment.
- Phase: pivotal.
- Number of sites: approximately 20 centers.
- Total enrollment from each site to be no more than 20% of the total sample size.
- Duration for each subject: participation in this study will start at day 3-21 post-stroke and will last up to 180 ± 15 days post-stroke.

NOTE: Sponsor's representative(s) may be present during study interventions, in-person or via combined audio and video remote conferencing or audio only, if video is not available. Presence of the Sponsor during procedures is for observational purposes only and is predicated on the premise of benefit to subject's well-being, as exemplified in the Guidelines on Good Clinical Practice specific to Advanced Therapy Medicinal Products (ATMP) issued by the European Commission https://ec.europa.eu/health/sites/health/files/files/eudralex/vol-10/atmp_guidelines_en.pdf.

Despite of its non-binding nature, EU-only application, and non-universal scope, it shows that there are conditions where subject's well-being may benefit from Sponsor's presence and this would not be considered unethical.

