8 STUDY ASSESSMENTS AND PROCEDURES

8.1 EFFICACY ASSESSMENTS

The order of and timeline of the screening procedures and evaluations (Visit 1) are presented in the study schema (please refer to § 1.2) and the schedule of activities (please refer to § 1.3).

The questionnaires and functional tests detailed below are appended to this protocol (please refer to § 12.1).

mRS (first screening procedure after consent is obtained)

The mRS is a 7-level scale with possible scores ranging from 0 (no symptoms at all) through 5 (severe disability) and 6 (death) and is used for measuring the degree of disability or dependence in the daily activities of people who have suffered a stroke or other causes of neurological disability (76). The mRS is the most frequently used outcome measure in stroke trials (77). To increase outcome comparability and minimize bias, the modified Rankin Scale assessments of global disability will be obtained at all sites using the formal, algorithmic Rankin Focused Assessment-Ambulatory (RFA-A) method by RFA-A-certified raters (78-80). The formal RFA-A elicitation technique is an NIH trial-developed method for assigning mRS scores validated to improve inter-rater reliability in assigning mRS scores. In addition, the RFA-A method to assign mRS scores has been employed for primary and second endpoint ascertainment in numerous FDA-regulated drug and device trials (47, 81-83).

Fugl-Meyer Assessment-Upper extremity (FMA-UE; second screening procedure)

The Fugl-Meyer Assessment is a stroke-specific, performance-based impairment index. It is designed to assess motor functioning, balance, sensation and joint functioning in patients with post-stroke hemiparesis (84, 85). It is frequently applied clinically and in research to determine disease severity, describe motor recovery, and to plan and assess rehabilitation treatment (86). This test is one of the most used instruments in rehabilitation and its validity and reliability has established validity, reliability, and sensitivity to treatment-related change (84, 87, 88).

In this study, the index will be used to assess the motor impairment of the upper extremity after stroke. Each movement will be graded on a 3-point scale, and the total score will range 0–66 points, with a higher score representing more active movements.

	The efficacy of a frequency-tuned electromagnetic field treatment in facilitating the recovery of subacute ischemic stroke patients – a pivotal study		

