9.2 SAMPLE SIZE DETERMINATION

A sample size is calculated to test the null hypothesis with 80% power at a 5% two-sided level of significance using a two sample-t-test for simplicity, even though the main statistical analysis may employ a statistically more powerful model-based approach. The estimates used for the mean and standard deviation of the changes from baseline to day 90 are taken from the literature as well as company pilot study data. In the pilot study, the mean change in mRS score from baseline to week 9 in the treatment group was -2.5 (SD=0.66) versus -1.3 (SD=0.46) in the sham group. In the literature a difference of 0.06 points on the mRS between treatment groups is considered clinically meaningful (114). As powering the trial to detect this difference would yield infeasibly large sample sizes, sample size projections were based on detecting a difference as low as 40% of the difference seen in the pilot trial = 0.5-point. To detect a 0.5-point difference between the groups with 80% power at a 5% level of significance using a standard deviation of 1 point and 1:1 allocation ratio, the calculated sample size (PROC POWER in SAS V9.4) is 128 participants in total, 64 participants in each arm. Allowing for a 15% dropout, 150 participants should be randomized.

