The principal statistical analysis will be a comparison between the treatment groups, derived from the visit by treatment group interaction term from the model. The adjusted mean change from baseline in mRS scores at the 90 days post-stroke visit will be estimated from the model (LS Means) interaction term for each group as well as for the difference between the adjusted means and presented together with 95% confidence intervals and level of significance.

The null hypothesis will be rejected in favor of the alternative hypothesis and the study deemed successful if the P value is <0.05 and the mean change mRS in the BQ 2.0 group is higher than that of the sham group at the 90 days post stroke visit.

A shift analysis of the primary endpoint will be performed as a sensitivity analysis as well.

Handling of Missing Primary Endpoint Data

By the 90 days post-stroke visit, we do not expect a high proportion of dropouts, as a placebo effect of the sham treatment is expected and was taken into consideration in the design of the study by using conservative estimates of the treatment effect.

All subjects with at least 1 post-baseline measurement will be included in the statistical analyses. The primary endpoint will be analyzed using a likelihood based repeated measures model, which can handle data missing at random.

For the mITT set, missing primary outcome data at day 90 will be imputed with multiple imputation using a model incorporating key baseline prognostic features as well as the last post-randomization observed value (LOV) of that endpoint (115). The LOV is defined as the last available post baseline visit data up to and including the last treatment visit or termination visit. The LOCF imputation method will also be used to carry forward the most recent data prior to withdrawal/dropout as a sensitivity analysis.

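### The primary success rule points the wrong way: it requires a higher mean mRS change on BQ 2.0, which on this scale means less recovery than sham

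*Protocol*

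**What the plan says.** The primary endpoint is the change in mRS from baseline to 90 days post-stroke. Section 8.1 gives the orientation of the scale: "The mRS is a 7-level scale with possible scores ranging from 0 (no symptoms at all) through 5 (severe disability) and 6 (death"). Lower is better.

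Section 9.2 reports the pilot changes with a sign. The mean change "in the treatment group was -2.5 (SD=0.66) versus -1.3 (SD=0.46) in the sham group". Improvement is therefore negative in the statistical section.

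Section 9.1 states a two-sided alternative: the mean changes are unequal. Section 9.4.2 says the model will estimate the adjusted (LS) mean change from baseline in each group and the difference between them. It then sets two conditions for rejecting the null and calling the study successful: p below 0.05, and "the mean change mRS in the BQ 2.0 group is higher than that of the sham group" at the 90-day visit.

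Section 4.1 states the hypothesis in words: "improvement in mRS score from baseline to 90 days post-stroke will be greater in patients allocated to active stimulation" than in those allocated to sham.

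**The concern.** The quantity tested is a signed change on a scale where a lower score is better. If improvement is negative, the higher of two mean changes is the less negative one, and the group that has it recovered less. Read literally, the rule credits BQ 2.0 when it does worse than sham.

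Three things depend on this sentence:

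- **Direction of the claim.** The alternative hypothesis has no direction and the test is two-sided, so this clause is the only part of the decision rule that turns a significant difference into a claim of benefit.
- **The secondary endpoints.** Section 9.4.1 allows secondary testing only once the primary null is rejected, and Section 9.4.2 makes rejection depend on the direction clause. Taken literally, a significant benefit closes the gate to all six secondary endpoints and a significant harm opens it.
- **The interim analysis.** Section 9.4.6 computes conditional power from the BQ 2.0 versus sham difference in mean change from baseline, without stating a sign. That text is not itself reversed, but it needs the same convention as the final rule.

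**Working it through.** **Inputs.** From Section 9.2: difference 0.5 points, SD 1, 1:1 allocation, two-sided 5% level, 80% power, 15% dropout; pilot mean changes -2.5 and -1.3. From Section 8.1: scale orientation. From Section 9.4.2: the success rule. From Section 2.2.2: pilot response percentages.

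**1. The plan's own sample size.** The power of a two-sample t-test comes from the noncentral t distribution with df = 2n - 2 and noncentrality δ / (SD × √(2/n)).

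- n = 64 per arm: df = 126, noncentrality 0.5 / √(2/64) = 2.83, power 80.1%.
- n = 63 per arm: power 79.5%, just short.

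So 64 per arm, 128 in total, is reproduced. For dropout, 128 / 0.85 = 150.6, against the stated 150, which is close enough.

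**2. What the sign in Section 9.2 means.** Section 2.2.2 gives 13 active and 8 sham completers.

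- Active: 54% improved by 3 points (7 patients) and 92% by at least 2 (12 patients, so 5 improved by exactly 2). Taking the remaining patient as improving by 1, the mean improvement is (7×3 + 5×2 + 1×1)/13 = 32/13 = 2.46, SD 0.66.
- Sham: 25% improved by 2 points (2 patients). Taking the other 6 as improving by 1, the mean improvement is (2×2 + 6×1)/8 = 10/8 = 1.25, SD 0.46.

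These match the sizes and SDs in Section 9.2, where they carry a minus sign. Negative change is improvement. Treating the remaining patients as improving by exactly 1 point is an assumption, but it reproduces both means and both SDs.

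**3. The pilot result against the rule.** BQ 2.0 minus sham = -2.5 - (-1.3) = -1.2. The BQ 2.0 change is lower, so on the Section 9.2 signs the result that motivated this trial fails the direction clause.

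**4. Probability of meeting each version of the rule.** Let D be the true BQ 2.0 minus sham difference in signed mean change, so negative is benefit. Each entry is the probability that two-sided p < 0.05 and the estimate lies in the stated direction, with SD 1.

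| True D | n per arm | Significant and BQ 2.0 higher (rule as written) | Significant and BQ 2.0 lower (direction corrected) |
|---|---|---|---|
| -0.5 (design benefit) | 64 | 9.3 × 10⁻⁷ | 80.1% |
| -0.33 | 146 (maximum, 292 in total) | 9.2 × 10⁻⁷ | 80.2% |
| 0 | 64 | 2.5% | 2.5% |
| +0.5 (harm) | 64 | 80.1% | below 0.01% |

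The two columns change places when the sign of D changes. Alpha, power and sample size are the same under either direction; only the outcome that counts as success differs.

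**The case against.** The best defence is that the protocol uses the word change in two ways. Section 2.2.2 reports the same pilot endpoint without a sign: the treatment group "experienced a mean change of 2.5 points, compared to 1.3 points in the sham group". On that usage a higher mean change is a greater improvement, the pilot would pass, and Section 9.4.2 would agree with Section 4.1. The intent is also plain from the primary objective, which is to reduce disability. The signed estimate and its confidence interval will be reported, so harm is unlikely to be presented as benefit in practice. Finally, Section 9.4.1 gives the SAP precedence where the two documents conflict.

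Much of this stands. It is very probably a wording error, and the 80.1% under harm is the design power with the sign reversed, not a forecast that harm would be claimed as success.

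It does not rescue the sentence. Section 2.2.2 is background. The statistical section uses signed values, and the rule follows directly on a description of adjusted mean change from baseline. Nothing in Section 9 redefines change as baseline minus Day 90 or as an absolute size. The SAP was not available for this review and cannot be assumed to correct the rule. Precedence would in any case leave a misstated success criterion in the protocol.

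**Conclusion.** The concern holds. On the scale in Section 8.1 and the signs in Section 9.2, the success rule in Section 9.4.2 is reversed and contradicts Section 4.1. Applied literally at the design effect with 64 per arm, it would almost never recognise a true benefit (probability 9.3 × 10⁻⁷) and would accept an equal harm 80.1% of the time.

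These figures assume SD 1, the two-sample t-test used for sample sizing, and change defined as Day 90 minus baseline. The reversal itself depends only on the last of these. It must be corrected because no other part of the decision rule fixes the direction of success, and a correction made after unblinding would look like a post-hoc change.

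**What to change.** Replace the direction clause in Section 9.4.2 with wording to this effect: *Change is defined as the Day 90 score minus the baseline score. The study is successful if the two-sided p-value is below 0.05 and the adjusted mean change in mRS at Day 90 is lower (more negative, that is, greater improvement) in the BQ 2.0 group than in the sham group, so that the LS-mean difference, BQ 2.0 minus sham, is below 0.*

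An equivalent repair is to define improvement as baseline minus Day 90 and keep the word higher. Whichever is chosen, state the same sign for the effect that enters conditional power in Section 9.4.6, and confirm that the SAP uses it.

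The cost is one sentence in the protocol, matched in the SAP if it carries the same rule. No patients or analyses are added, and sample size, alpha and power do not change. It should be done before any unblinded data are seen, including the interim analysis.

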9.4.3 ANALYSIS OF THE SECONDARY ENDPOINT(S)

The hierarchy approach will be adopted for the primary and secondary endpoints to control type I error due to multiple endpoint testing. The order of the secondary endpoints is specified above in § 9.4.13.

The change from baseline in FMA-UE, BBT, SIS Hand Domain, SIS-16 and 10MWT, and the EQ-5D-5L score at day 90, will be compared between the groups with analysis of variance adjusting for baseline value, if relevant (§ 9.4.2).

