6.3 MEASURES TO MINIMIZE BIAS: RANDOMIZATION AND BLINDING

6.3.1 ALLOCATION TO STUDY INTERVENTION

After informed consent has been elicited from the subject or his/her legally authorized represented, and the subject is determined to fully meet the study eligibility criteria, he/she will be equally allocated (with a 1:1 ratio) to one of the following 2 treatment groups based on a permuted block randomization scheme with blocks stratified by site, age (22-69, 70-85) and mRS score at baseline (3 vs 4):

- BQ 2.0 active stimulation group
- BQ 2.0 sham stimulation group

Allocation (randomization) of participants to study groups will proceed through the use of the EDC system (Syncrony) for randomization and the BQ 2.0 Administrator Panel for treatment allocation. The site personnel (Study Coordinator or specified designee) will be required to enter or select information including but not limited to the user's ID and password, the protocol number, and the participant number. The site personnel will then be provided with a group assignment and randomization number. The Syncrony system will provide to the unblinded site personnel the study intervention allocation assigned. The randomization schedule and treatment arm assignments will be kept by Syntactx-NAMSA data manager with appropriate security measures and access control.

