8.1.1.4 MIDTERM FOLLOW-UP VISIT (IN CLINIC)

This visit will take place in the clinic (± 4 days from the 20th treatment). Though, in special circumstances and subject to the approval of the Principal Investigator, the visit can be conducted in an out-patient setup or via combined audio and video remote conferencing or audio only, if video is not available.

The following assessments (described in § 8.1) will be performed during this visit:

- mRS,
- FMA-UE,
- BBT,
- SIS Hand Domain,
- SIS-16

At this visit, the following data will be collected as well:

- Vital signs
- Any changes in concomitant medications
- Any adverse events
- Any device deficiencies
- PT/OT activities performed outside of study since last visit
- Use of healthcare resources

	The efficacy of a frequency-tuned electromagnetic field treatment in facilitating the recovery of subacute ischemic stroke patients – a pivotal study		
	No. BQ5	Ver. 4	Page 65 of 150

At this visit day, a treatment session may or may not take place, in accordance to the availability of the subject and/or the site. If a session will not take place, and unless completed over the weekend, 4 treatment sessions will take place in that week.

If a treatment session is to take place at the same day of the assessment, the session may be conducted only after the assessments were completed to avoid changing outcome measure scores due to subject fatigue.

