9.4.2 ANALYSIS OF THE PRIMARY ENDPOINT

The primary endpoint, mRS change from baseline (day 4-21 post-stroke) to 90 days post-stroke, will be compared between the treatment groups using repeated measures analysis of covariance (ANCOVA, SAS® MIXED procedure).

The model will include the following fixed effects: treatment group, visit [categorical – midterm follow-up visit (± 4 days from 20th treatment) and Day 90 follow-up visit (day 90 ± 15 days post-stroke)], treatment group by visit interaction with baseline mRS and age entered as covariates. Age will be entered as a continuous variable so that the potential for co-linearity problems will be minimized. Center will be entered as a random effect. The treatment group by site interaction will be evaluated as well, but not as part of the principal statistical evaluation.

The compound symmetry covariance structure will be used. If the model does not converge, then either the unstructured or autoregressive (AR1) (whichever model has the lower Akaike information criterion statistic) covariance matrix structure will be used instead. At this time point (up to 3 months post stroke), we do not expect a high proportion of dropouts, as a placebo effect of the sham treatment is expected and was taken into consideration in the design of the study. Thus, any missing data at this time point can be considered missing at random. Therefore, since likelihood based repeated measures is also an imputation method, for this evaluation no other method of imputation of missing data is considered beyond the model estimates. Nevertheless, should the missing at random assumption prove to be incorrect, a sensitivity analysis using methods for data imputation may be performed, such as last observed value (LOV) of that endpoint (115). The LOV is defined as the last available post baseline visit data up to and including the last treatment visit or termination visit. Additionally, we may consider multiple

	The efficacy of a frequency-tuned electromagnetic field treatment in facilitating the recovery of subacute ischemic stroke patients – a pivotal study		
	No. BQ5	Ver. 4	Page 81 of 150

imputation using a model incorporating key baseline prognostic features as well as the last post-randomization if deemed necessary.

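### Section 9.4.3 names a baseline-adjusted analysis of variance for the secondary endpoints that, on its natural reading, leaves out the stratification factors and, for four of the six, the midterm measurement

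*Protocol*

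**What the plan says.** Section 9.4.3 covers the change from baseline in FMA-UE, BBT, SIS Hand, SIS-16 and 10MWT, and the day-90 EQ-5D-5L score. These "will be compared between the groups with analysis of variance adjusting for baseline value, if relevant", followed by a bracketed reference to section 9.4.2. No other model term is named.

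Section 9.4.2 gives the primary endpoint a fuller model. It "will be compared between the treatment groups using repeated measures analysis of covariance (ANCOVA, SAS® MIXED procedure"), with midterm and day-90 visits, "treatment group by visit interaction with baseline mRS and age entered as covariates". It adds: "Center will be entered as a random effect".

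Section 6.3.1 randomizes in permuted blocks "stratified by site, age (22-69, 70-85) and mRS score at baseline (3 vs 4").

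Section 8.1.1.4 schedules the midterm visit ("This visit will take place in the clinic (± 4 days from the 20th treatment")) and lists mRS, FMA-UE, BBT, SIS Hand and SIS-16. Neither 10MWT nor EQ-5D-5L is assessed there. The Schedule of Activities has EQ-5D-5L only at days 90 and 180, so it has no baseline.

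Section 9.4.1 orders the secondaries in a fixed testing hierarchy, says in general terms that methods will be adapted when a subject has several measurements, and leaves detailed methods to an SAP that overrides the protocol. The SAP was not available for this review.

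**The concern.** The protocol builds a good model for its primary endpoint and then names a plainer one for the secondaries, although the covariates are already collected for every subject and the midterm scores are scheduled for four of the six endpoints. Two things are given up.

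- **Stratification factors, all six endpoints.** Site, age and baseline mRS were chosen for stratification because they are expected to predict outcome. Leaving them out of the model keeps their variation in the error term.
- **Midterm measurement, four endpoints.** A repeated-measures model lets a subject with a midterm but no day-90 value contribute. A day-90 comparison does not. The multiple-imputation rule and the rule on at least one post-baseline value both stand under the missing-data heading for the primary endpoint.

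Because testing is in fixed order, an avoidable miss on FMA-UE or BBT closes every endpoint below it.

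**Working it through.** **The plan's own figure.** Section 9.2 (primary endpoint): difference 0.5, SD 1, two-sided 5%, 80% power. A two-sample t-test gives 64 per arm, 128 in total, with power 80.1%. Then 128/0.85 = 150.6, against 150 stated. The figure reproduces and is not in dispute. The protocol gives no effect size, SD or power for any secondary endpoint, so everything below is illustrative.

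**Base case (assumed).** Standardized effect 0.5, 75 randomized per arm (150/2), 64 observed and 11 dropouts. Normal approximation: power = Φ(0.5·√(64/2) − 1.96) = Φ(2.828 − 1.96) = 80.7%.

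**(a) Stratification factors.** If they explain an added share R² of the residual variance, the SD becomes √(1 − R²):

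| Added R² (assumed) | Power | Gain (points) |
|---|---|---|
| 0.05 | 82.7% | 2.0 |
| 0.10 | 84.6% | 3.9 |
| 0.20 | 88.5% | 7.8 |

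For example, at R² = 0.10, 2.828/√0.90 = 2.981 and Φ(2.981 − 1.96) = 84.6%. When assignment has been balanced on a prognostic factor, an analysis that omits it overstates the standard error. The error is conservative, so type I error is not inflated.

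**(b) Midterm data.** With dropout missing at random, the variance of a day-90 arm mean is SD²·[(1 − ρ²)/64 + ρ²/n_mid]. Here ρ is the midterm to day-90 correlation (assumed), and n_mid counts subjects with a midterm value:

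| Dropouts with a midterm value | n_mid | Power, ρ = 0.5 | ρ = 0.7 | ρ = 0.8 | ρ = 0.9 |
|---|---|---|---|---|---|
| none | 64 | 80.7% | 80.7% | 80.7% | 80.7% |
| half | 69.5 | 81.5% | 82.3% | 82.7% | 83.2% |
| all | 75 | 82.2% | 83.5% | 84.4% | 85.4% |

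For example, with all dropouts and ρ = 0.8, 0.36/64 + 0.64/75 = 0.01416. That is an effective 70.6 per arm and power 84.4%. The gain runs from 0 to 85.4 − 80.7 = 4.7 points. It is zero for 10MWT and EQ-5D-5L, which have no midterm value.

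**(c) Bias in a completers analysis.** Simulation with 1,000,000 subjects per arm, no treatment effect, 15% dropout in each arm, and logistic dropout with slope 1 per SD of the midterm score (or 0), for ρ = 0.5 to 0.8:

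| Dropout mechanism | Size of bias |
|---|---|
| same in both arms | about 0 (at most 0.003 SD) |
| depends on midterm in sham only | 0.07 to 0.11 SD |
| opposite directions in the two arms | 0.13 to 0.21 SD |

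As simulated, with poor scorers leaving sham, the bias runs against the device. With the arms exchanged it would favour it.

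**(d) What the pointer to 9.4.2 can mean.** Section 9.4.9 uses the same phrase and the same pointer for MoCA, ALDS and PHQ-8. These are scheduled only at day 90, so there the pointer cannot bring in a repeated-measures model. That favours baseline adjustment at one visit as the natural reading of 9.4.3, without proving it.

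**The case against.** The best defence is that 9.4.3 does not fix a single-visit analysis. It points to the repeated-measures section. Section 9.4.1 promises adaptation for within-subject correlation. Section 9.3 makes mITT the principal set for secondaries too. Nothing says that subjects without day 90 are dropped, and covariate lists and missing-data rules normally belong in the SAP.

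Much of this stands. A reader might infer that the protocol commits the secondaries to a biased completers-only analysis. It does not: that is an inference from the named method, and the bias also needs dropout to act differently by arm. Three other strong readings fail as well.

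- The midterm point does not cover all six endpoints. 10MWT and EQ-5D-5L have no midterm value to ignore.
- No EQ-5D-5L baseline is overlooked. None is collected, and the where-relevant qualifier covers that case.
- The 80% benchmark belongs to mRS, so nobody can say the secondaries fall short of a promised power.

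Nor is the named method crude. Change adjusted for baseline is in effect an ANCOVA for five of the six endpoints.

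The defence does not remove the point. The protocol is not silent: it names a method, and that method is weaker than the one it uses for its primary endpoint. The sentence in 9.4.1 names no model, and the pointer is ambiguous for the reason given in (d).

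**Conclusion.** The point holds as a free improvement. As worded, section 9.4.3 adjusts each secondary only for its own baseline, where there is one. On its natural reading it omits site, age and baseline mRS for all six endpoints and the midterm value for FMA-UE, BBT, SIS Hand and SIS-16.

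The size is modest and cannot be fixed from the document. Omitting the strata costs about 2 to 8 power points (assumed added R² 0.05 to 0.20). Omitting midterm data costs 0 to about 5 points (assumed ρ 0.5 to 0.9, and from none to all of the dropouts with a midterm value). Both start from an assumed base of 80.7%. Type I error is not inflated. Bias is a risk only under an arm-differential dropout mechanism, which the protocol gives no reason to expect or to exclude.

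**What to change.** In section 9.4.3, or in the SAP if it governs, before unblinding:

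- **FMA-UE, BBT, SIS Hand, SIS-16:** a repeated-measures model as in 9.4.2, with midterm and day-90 visits, treatment by visit, own baseline, baseline mRS, age and random center, and the day-90 contrast as the test. Check that the covariance structure suits these scales. Section 9.4.2 starts from compound symmetry, which assumes equal variance at both visits. Unstructured is feasible, since two visits need only two variances and one covariance.
- **10MWT:** ANCOVA of the change with own baseline, baseline mRS, age and center.
- **EQ-5D-5L at day 90:** ANCOVA with baseline mRS, age and center. Baseline SIS-16 is an optional further covariate.
- **The pointer:** replace the bare reference to 9.4.2 with a statement of what is carried over. The same section cites 9.4.13 for the testing order, which stands in 9.4.1. Correct that in the same edit.

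The cost is wording only. All the variables are already scheduled, no visit or sample size changes, and the added terms use few degrees of freedom.
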